7.2.16 Other Safety Variables

External Ocular Examination (EOE)

External Ocular Examination assesses the motility of the extraocular muscles and the appearance and function of the eyelids before the instillation of any dilating or anesthetic eye drops. *Clinically significant changes (or a clinically significant worsening) in EOE, which were observed the first time during study will be reported as adverse event.*

Motility of extraocular muscle and appearance/function of eye lids is assessed separately for each eye at Screening Visit, Baseline Visit 0hr, D1 8hr, D2 Pre-Dose, D2 8hr, D3 Pre-Dose, D6 Pre-Dose, D6 8hr, FU1 0hr, FU2 8hr, FU3 0hr and is recorded on the eCRF pages “External Ocular Examination” and “Appearance and Function of Eyelids”.

For the analysis, the motility of the extraocular muscle will be evaluated by the field of movements Right and up (‘Normal’, ‘Abnormal’), Right (‘Normal’, ‘Abnormal’), Right and Down (‘Normal’, ‘Abnormal’), Left and Up (‘Normal’, ‘Abnormal’), Left (‘Normal’, ‘Abnormal’), Left and Down (‘Normal’, ‘Abnormal’) as documented at the eCRF. No imputation will be envisaged for these parameters.

Appearance and function of eyelids will be summarized by the following parameters:

- Incidence of proven eyelid deformity/abnormality, which will be considered as present, if the question “Evidence of eyelid deformity or abnormality” on the eCRF page “Appearance and Function of Eyelids” is answered ‘Yes’.

- Incidence of abnormal motor function of eyelids (i.e. upper lid elevation and forceful lid closure), which will be considered as present, if the question “Motor function of eyelids” on the eCRF page “Appearance and Function of Eyelids” is answered ‘Abnormal’.
- Incidence of corneal exposure in case of closed eyelids, which will be considered as present, if the question “Is there corneal exposure when the eyelids are closed?” on the eCRF page “Appearance and Function of Eyelids” is answered ‘Yes’.
- Incidence of proven punctal occlusion, which will be considered as present, if the question “Is there evidence of punctal occlusion?” on the eCRF page “Appearance and Function of Eyelids” is answered ‘Yes’.
- Incidence of punctal plugs, which will be considered as present, if the box “Punctal plugs” is ticked on the eCRF page “Appearance and Function of Eyelids”.
- Incidence of thermal or surgical occlusion, which will be considered as present, if the box “Thermal or surgical occlusion” is ticked on the eCRF page “Appearance and Function of Eyelids”.
- Incidence of Other punctal occlusion, which will be considered as present, if the respective “Other” box is ticked on the eCRF page “Appearance and Function of Eyelids”.

Slit Lamp Examination

Slit lamp examination was performed separately for each eye at Screening Visit, Baseline Visit 0hr, D1 8hr, D2 Pre-Dose, D2 8hr, D3 Pre-Dose, D6 Pre-Dose, D6 8hr, FU1 0hr, FU2 8hr, FU3 0hr and is recorded on the eCRF page “Slit Lamp Examination (Biomicroscopy)”.

The following assessments will be performed:

Eye Structure	Rating
Eye Lid - Meibomian Glands	0 = None (none are plugged) 1 = Mild (1 to 2 glands are plugged) 2 = Moderate (3 to 4 glands are plugged) 3 = Severe (All glands are plugged)
Eye Lid – Erythema	0 = None (normal) 1 = Mild (redness localized to a small region of the lid(s) margin OR skin) 2 = Moderate (redness of most of all of lid margin OR skin) 3 = Severe (redness of most or all of lid margin AND skin) 4 = Very Severe (marked diffuse redness of both the lid margin AND skin)
Eye Lid – Edema	0 = None (normal) 1 = Mild (localized to a small region of the lid) 2 = Moderate (diffuse, most or all lid but not prominent/protruding) 3 = Severe (diffuse, most or all lid AND prominent/protruding) 4 = Very Severe (diffuse AND prominent/protruding AND reversion of the lid)

Eye Structure	Rating
Lashes	0 = Normal 1 = Abnormal (specify)
Conjunctiva – Erythema	0 = None (normal) 1 = Mild (a flush reddish color predominantly confined to the palpebral or bulbar conjunctiva) 2 = Moderate (More prominent red color of the palpebral or bulbar conjunctiva) 3 = Severe (definite redness of palpebral or bulbar conjunctiva))
Conjunctiva – Edema	0 = None (normal) 1 = Mild (slight localized swelling) 2 = Moderate (moderate/medium localized swelling or mild diffuse swelling) 3 = Severe (severe diffuse swelling) 4 = Very severe (very prominent/protruding diffuse swelling)
Lens	0 = No Opacification (normal lens) 1 = Mild Lens Opacification 2 = Moderate Lens Opacification 3 = Severe Lens Opacification 4 = N/A Subject with Artificial Lens In addition there is also a field to specify Other findings
Iris	0 = Normal 1 = Abnormal
Anterior Chamber Inflammation	0 = None (no Tyndall Effect) 1 = Mild (Tyndall Effect barely discernable) 2 = Moderate (Tyndall beam in the anterior chamber is moderately intense) 3 = Severe (Tyndall beam in the anterior chamber is severely intense)
Other	Specification and assessment of other investigated eye structure

For each eye structure, the investigator will have the opportunity to tick also ‘Not done/Not evaluable’, which will be treated as ‘Missing’ for analysis purposes.

Clinically significant changes (or a clinically significant worsening) in SLE, which were observed the first time during study will be reported as adverse event.

All grading assessments of different eye structures will be evaluated as collected on the eCRF. No imputation will be envisaged for these parameters.

No aggregated presentation is planned for other assessments done during Slit lamp evaluation.

Fundus Ophthalmoscopy

Fundus ophthalmoscopy to assess the eye structure will be performed and results recorded on the eCRF page “Fundus Ophthalmoscopy” by utilizing the following assessments.

Eye Structure	Rating
Vitreous	0 = Normal 1 = Abnormal (specify) 2 = Not done/Non-Evaluabe
Retina / Macula	0 = Normal 1 = Abnormal (specify) 2 = Not done/Non-Evaluabe
Choroid	0 = Normal 1 = Abnormal (specify) 2 = Not done/Non-Evaluabe
Optic Nerve	0 = Normal 1 = Abnormal (specify) 2 = Not done/Non-Evaluabe
Cup/Disc Ratio	0 = Normal 1 = Abnormal (specify) 2 = Not done/Non-Evaluabe In addition, the Cup/Disc Ratio is recorded

Dilated FO will be performed at Screening Visit with non-dilated FO performed at Baseline Visit 0 hr, FU2 8hr and FU3 0hr. Clinically significant changes (or a clinically significant worsening) in FO, which were observed the first time during study will be reported as adverse event.

Physical Examination

Physical Examination includes an examination of general appearance, head-eyes-throat-nose-ears (HEENT), skin, thorax/lungs, cardiovascular system, abdomen, lymph nodes, musculoskeletal system, neurological system and other examinations as necessary.

The clinical evaluation ('Normal', 'Abnormal, Not Clinically Significant', 'Abnormal, clinically significant'). It is collected on eCRF Page "Physical Examination" at Screening Visit, Baseline Visit, FU1, FU2 and FU3.

Clinically significant abnormalities (or a clinically significant worsening of a physical condition), which were observed the first time during study will be reported as adverse event.

7.2.17 Pharmacokinetic Endpoints

Two validated ELISA tests performed at Dompé farmaceutici s.p.a. will be used for PK measurements. The original validated method (ELISA I) will be the same applied to the NGF determination in serum samples taken from studies NGF0112 and NGF0212. A new additional validated ELISA method (ELISA II) will be performed with the intention of improving the sensitivity in the determination of NGF serum levels.

Pharmacokinetics blood samples were taken on Baseline Visit 0 hr, 0.5 hr, 2 hr, 4 hr, 8 hr, 9 hr, 10 hr, 11 hr, 12 hr, 14 hr and 16 hr, for assessment of single dose scheme at D1 Pre-Dose, 0.5 hr, 2 hr, 4 hr, 8 hr, 9 hr, 10 hr, 11 hr, 12 hr, 14 hr and 16 hr, for multiple dose scheme at D2 Pre-Dose, 0.5 hr, 2 hr, 4 hr, 6hr, 8 hr, 9 hr, 10 hr, 10.5hr, 11 hr, 12 hr, 13hr, 14 hr and 16 hr, D3 Pre-Dose, 2 hr, 4 hr, 6 hr, 8 hr, 10 hr, D4 Pre-Dose, D5 Pre-Dose, D6 Pre-Dose, 4 hr, 8 hr, 10 hr, 10.5hr, 11 hr, 12 hr, 13 hr, 14 hr and 16 hr, FU1 0hr, FU2 0 hr and 8 hr, FU3 0hr.

The assessment times are documented on eCRF Pages “Pharmacokinetics – Anti-Therapeutic Antibodies”, the rhNGF serum concentration assessed via both ELISA methods will be provided as external Excel files by Dompé. To maintain masking, these files will be provided for BDRM purposes in a masked manner by utilizing a dummy subject identification. For the final analysis, the Excel Files will contain the correct subject identification number.

The concentration versus time profiles of NGF will be assessed from individual serum samples of all subjects. As a general principle, the nominal assessment times will be used.

For the rhNGF serum levels according to ELISA I and ELISA II time-matched changes from baseline will be presented for the PKS (excluding blood samples at 6 hr, 10.5hr and 13 hr).

For this purposes, values below the limit of detection will be set to a value of 1 pg/ml. However, for listings values below the limit of detection will be presented as “< 32 pg/ml” for ELISA I levels and ‘< 15 pg/ml’ for ELISA II.

A binary variable ‘Presence of rhNGF’ will be derived for each ELISA with ‘No’ indicating a value below the limit of detection and ‘Yes’ indicating a value above the limit of detection.

Beyond the respective rhNGF plasma levels for both ELISA methods, the following parameters will only be investigated for each ELISA method, if the data warrant to do so:

- *maximum observed serum concentration (C_{max}), time to reach C_{max} (t_{max}), time elapsed between dosing and the first serum concentration that exceeds the assay quantification limit (t_{lag}) as measured without treatment based on assessments on D-1*
- *C_{max} , t_{max} , t_{lag} of single dose regimen based on assessments on D1 and pre-dose of D2*
- *C_{max} , t_{max} , t_{lag} of multiple dose regimen based on assessments atating with pre-dose of D2*
- *serum concentration measured before the administration of the next dose (C_{trough}) as assessed at pre-dose visit on D2, D3, D4, D5, D6*
- *$AUC_{[0-24]}$ for the single dose regimen and the first day of multiple dose regimen. $AUC_{[0-24]}$ as area under the serum concentration versus time curve from time 0 h to pre-dose value of the next day calculated by the linear trapezoidal rule. Values below the level of quantitation will be set to 0. Values below the baseline concentration will be set to zero other than for the values for which no later values above the baseline concentration are available, which will be set to missing.*
- *$AUC_{0-t_{last}}$ for the multiple dose regimen. This is derived as area under the serum concentration versus time curve from time 0 h to the last data point t_{last} after drug administration above the limit of quantitation and the baseline concentration, calculated by the linear trapezoidal rule.*

Values below the baseline concentration will be set to zero other than for the values for which no later values above the baseline concentration are available, which will be set to missing

- *AUC for the multiple dose regimen. AUC will be derived as area under the serum concentration versus time curve extrapolated to infinity, calculated as $AUC = AUC_{0-t_{last}} + C_{last}/\lambda_z$*

The kinetics of single dose administration as well as multiple dose assessment will be evaluated.

The analysis of pharmacokinetic parameters will be based on the difference between the measured rhNGF value after dosing and the value measured at the corresponding time on Day -1.

Values below the limit of quantitation and missing values will be labeled and accounted for accordingly during evaluation.

Additional evaluations, such as compartmental analysis, may be performed with an exploratory purpose for the multiple dose regimen if the study data suggest that they are needed for a better understanding of the drug. Likewise, the pharmacokinetic results of this study may be later pooled with results of other studies for population pharmacokinetic and pharmacokinetic-pharmacodynamic analysis and modelling purposes.

If required, more details on the PK evaluation will be provided in an appendix to the SAP, which will be finalized before unmasking of the study.

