8.3.2 Handling of Dropouts or Missing Data

For the analysis, no imputation of data is planned; all data will be analysed as collected.

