10.9 Pharmacokinetic Evaluations

All pharmacokinetic evaluations will be presented for the PKS.

Summary descriptive statistics for both absolute and time-matched changes from baseline will be provided by treatment for rhNGF serum concentrations ELISA I as well as ELISA II at all scheduled time points including geometric mean, coefficient of variation and 95% confidence intervals for the geometric mean.

In addition, presence of rhNGF concentrations will be summarized by treatment group for ELISA I and ELISA II concentrations at each scheduled assessment time.

Serum concentration versus time profiles will be presented on linear and log/linear scale for each individual with at least one value above detection level as well as geometric mean and median values for each time-point by treatment group. For individual plots, actual sampling times will be used. For the plots of geometric mean, scheduled sampling times will be used.

All recorded PK data will be listed for the SAF, clearly indicating subjects not included in the PKS.

Further PK analysis might be performed according to an appendix of the SAP, if indicated.

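### SAP 7.2.17 sets undetected rhNGF values to 1 pg/ml for both assays (limits 32 and 15 pg/ml); where many values are undetected, that constant drives the geometric means, CVs, confidence intervals and time-matched changes

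*SAP*

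**What the plan says.** SAP 7.2.17 announces that for both assays "time-matched changes from baseline will be presented for the PKS (excluding blood samples at 6 hr, 10.5hr and 13 hr"). The next sentence is the substitution rule: "For this purposes, values below the limit of detection will be set to a value of 1 pg/ml". In listings, by contrast, such values "will be presented as “< 32 pg/ml” for ELISA I levels and ‘< 15 pg/ml’ for ELISA II". The section also keeps detectability as a variable in its own right: "A binary variable ‘Presence of rhNGF’ will be derived for each ELISA", summarised by treatment and time point in Tables 14.6-1.3 and 14.6-2.3.

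SAP 10.9 sets the output: "Summary descriptive statistics for both absolute and time-matched changes from baseline will be provided by treatment", "including geometric mean, coefficient of variation and 95% confidence intervals for the geometric mean". It gives no separate below-limit rule for absolute concentrations.

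Two other rules bear on this. For AUC[0-24], SAP 7.2.17 repeats protocol 10.1.1: "Values below the level of quantitation will be set to 0". SAP 8.3.2, on dropouts and missing data, says: "For the analysis, no imputation of data is planned; all data will be analysed as collected". The SAP gives no reason for choosing 1 pg/ml, no sensitivity analysis, and no maximum share of undetected values for reporting a geometric mean.

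**The concern.** A result known only to be below 32 or 15 pg/ml enters the summaries as 1 pg/ml, which is 1/32 or 1/15 of the limit. On the log scale, where geometric mean, CV and CI are calculated, the gap between the constant and the limit is ln 32 = 3.47 or ln 15 = 2.71. A few detected values among many undetected ones then produce a geometric mean far below anything the assay can measure, with a very large CV. In the change tables, a small movement across the limit is recorded as a large rise or fall.

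Heavy non-detection is plausible for ELISA I. Protocol 2.6 reports that rhNGF was detectable in only 6 subjects of the earlier healthy-volunteer study, and SAP 7.2.17 says ELISA I is the method used there.

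At stake are Tables 14.6-1.1, 14.6-1.2, 14.6-2.1 and 14.6-2.2 and the geometric-mean plots. Cmax, AUC and the other derived parameters are conditional on the data warranting them, so these tables are the PK output the plan commits to. A reader could take a geometric mean of 1.45 pg/ml for a measured level.

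**Working it through.** The plan states no figure that depends on this rule, so there is nothing to reproduce. The check is one of sensitivity.

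**Inputs from the documents.** Constant 1 pg/ml and limits (LOD) of 32 and 15 pg/ml (SAP 7.2.17); 20 subjects on rhNGF (protocol 6.1); 58 rhNGF-treated subjects in the earlier study and 6 subjects with detectable rhNGF (protocol 2.6).

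**Expected detection on ELISA I.** If all 6 were among the 58 treated, 6/58 = 10.3% (exact 95% CI 3.9-21.2%), or about 2 of 20. This counts subjects with any detected value, not samples.

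**Geometric mean, CI and CV.** Assumption: k of 20 values are detected, all at 40 pg/ml, on ELISA I; c is the value given to the rest.

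- GM = exp(m), with m = [k ln 40 + (20 - k) ln c]/20
- s² = [ln(40/c)]² × (k/20)(1 - k/20) × 20/19
- 95% CI = exp(m ± 2.093 s/√20)
- CV = √(exp(s²) - 1)

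For k = 2 and c = 1: m = 2 × 3.689/20 = 0.369, so GM = 1.45. s² = 13.61 × 0.09 × 20/19 = 1.289, so s = 1.135. The half-width is 2.093 × 1.135/4.472 = 0.531, so the CI is 0.85 to 2.46. CV = √(3.63 - 1) = 162%.

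| Detected of 20 | c = 1 | c = 16 (LOD/2) | c = 32 (LOD) |
|---|---|---|---|
| 2 | 1.45 (0.85-2.46), CV 162% | 17.5 (15.4-20.0), CV 29% | 32.7 (31.7-33.8), CV 7% |
| 10 | 6.3 (2.6-15.3), CV 591% | 25.3 (20.3-31.5), CV 50% | 35.8 (33.9-37.7), CV 11% |
| 18 | 27.7 (16.3-47.1), CV 162% | 36.5 (32.0-41.6), CV 29% | 39.1 (37.9-40.4), CV 7% |

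With none detected, c = 1 gives GM 1.00 and CI 1.00-1.00 for either assay. With all detected, the choice of c has no effect. Spreading the detected values around 1.5 × LOD (log-SD 0.3) gives the same picture: at k = 2, GM 1.47 and CV 178% with c = 1, against 17.9 and CV 35% with LOD/2. The corresponding ELISA II figures are 1.37 and CV 123%, against 8.4 and CV 35%.

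**Time-matched change.** A value going from undetected to the limit is scored as 32 - 1 = 31 (ELISA I) or 15 - 1 = 14 (ELISA II). The true change could be anything from near 0 up to the limit.

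Assume no drug effect, ELISA I, and lognormal endogenous NGF with median r × LOD and the within-subject CV shown. Let p = Φ[ln(1/r)/σ], with σ² = ln(1 + CV²), be the chance that a value is undetected. A pair crosses the limit with probability 2p(1 - p), and each crossing is scored as 31 pg/ml or more.

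| r | CV 10% | CV 20% |
|---|---|---|
| 0.8 | p = 0.987; 2.5% of pairs | p = 0.870; 23% |
| 1.0 | p = 0.5; 50% | p = 0.5; 50% |
| 1.2 | p = 0.034; 6.5% | p = 0.179; 29% |

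In simulation, true changes of that size occur in under 1% of pairs in every cell. At r = 1.0 and CV 10%, the SD of the change is 4.5 in truth, 23.9 with the planned rule and 13.4 with LOD/2.

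**The case against.** Several points on the other side stand.

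- **Scope.** A reader might infer that every undetected value becomes 1 pg/ml throughout. The documents do not support that: listings, the presence variable and AUC[0-24] follow other rules. The sentence itself refers back to time-matched changes. Extending it to absolute levels is a strong inference, since a geometric mean needs positive values, but it is not stated.
- **Detectability is already reported.** The presence tables, the median and range planned for all quantitative endpoints (SAP 8.1), and individual plots limited to subjects with a detected value would tell a reader how much was detected.
- **Most samples undetected?** One might take this as established. The protocol's 6 is a count of subjects on ELISA I. ELISA II was added to improve sensitivity, and no detection rate is given for it.
- **Half the limit is not the truth.** In the 2-of-20 example, 18 of the 20 values entering the 17.5 are copies of 16. A sample undetected by both assays gets 1 and 1 under the plan, but 16 and 7.5 under half-limits. At r = 1.0, half-limits still leave the SD of change well above the true value.
- **Half of all pairs showing a spurious change?** This is the worst case in the table, and the documents give no endogenous NGF level. If nearly everything is undetected, most changes are simply 1 - 1 = 0.
- **Contradiction with 8.3.2 and the AUC rule?** Section 8.3.2 concerns dropouts and missing data, and SAP 7.2.17 names below-limit and missing values separately. The AUC rule is protocol text, is conditional, and refers to quantitation. Using 1 instead of 0 over 24 h adds at most 1 × 24 = 24 pg·h/ml.

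These points narrow the concern but do not remove it. The change tables explicitly use the constant, and nothing restricts geometric mean, CV and CI to time points where they carry information.

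**Conclusion.** The concern holds in a limited form. Where a large share of values is undetected, the 1 pg/ml constant drives the geometric mean, CV, CI and time-matched changes. The effect is complete when nothing is detected, dominant when about half or more is undetected, and absent when everything is detected; even 2 undetected of 20 raises the CV several-fold. For ELISA I at the detection rate the earlier study suggests, the geometric mean could be 1.45, 17.5 or 32.7 pg/ml depending only on the constant. This rests on the assumed 40 pg/ml for detected values and on the rule applying to absolute levels. Artificial changes of 31 pg/ml or more would affect 2.5% to 50% of pairs under the assumed endogenous levels and variability. The size of the problem for ELISA II cannot be judged from the documents.

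Severity: should-fix. A reader might infer that the plan must not go ahead unchanged, but PK is the secondary objective, no inferential analysis is planned, no decision rule uses these tables, and the presence tables are unaffected.

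**What to change.** In SAP 7.2.17 and 10.9:

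1. Report geometric mean, CV and CI at a time point only where at least half of the values are at or above the assay's limit. Otherwise report the planned n (%) detected, with the median and range, showing undetected values as <32 or <15 pg/ml.
2. Where a number is needed, replace the common 1 pg/ml by an assay-specific value such as half the limit (16 and 7.5 pg/ml). State that it is a convention and show sensitivity to it, for example with 0 and with the limit itself. The zero version applies to arithmetic summaries and changes only, because a geometric mean needs positive values.
3. State whether the rule covers absolute concentrations as well as changes. Reconcile it with the protocol's set-to-0 rule for AUC, and use detection and quantitation consistently. A clause in 8.3.2 saying that below-limit assay values are handled in 7.2.17 would prevent misreading.

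Cost: SAP wording and slightly more programming, with no new data. Some time points will have no geometric mean, and the mean plots will have gaps there. Leaving the AUC rule as it stands avoids a departure from the protocol; changing it would have to be declared as one.

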2.3 Preclinical Pharmacokinetics

In Study A1122, Wistar rats were treated with rhNGF eye drops at ascending doses of 0.2, 0.4, 0.6, 0.8, and 1.2 mg/mL (3 times within one day, 3 hours apart) with a 3-day wash-out period between all administrations.

At the 0.2 mg/ml concentration, which is 10 fold that intended for clinical use, the results suggest systemic absorption following ocular administration. Disproportionately greater degrees of systemic exposure are seen at the higher doses used in animal toxicology studies.

In Study A1119, rhNGF was administered via eye drops (into both eyes) to one male and one female New Zealand White rabbit at ascending doses of 0.2, 0.4, 0.6, 0.8, and 1.2 mg/mL (3 times within one day, 3 hours apart) with 3-day wash-out periods between all administrations.

Overall the systemic absorption in rabbit was very marginal and not dose-proportional.

In the toxicokinetic analysis of the four-week ocular toxicity study in rats (Study A1129), only two from the potential three peak concentrations could be observed due to insufficient time-points.

Relative bioavailability of topical ocular NGF vs. an i.v. dose was estimated as follows:

- 12.8% – 20.7% at 0.6 mg/ml NGF.
- 21.5% - 35.7% at 0.8 mg/ml NGF.
- 22.8% - 70.9% at 1.2 mg/ml NGF (22.8% - 32.5% for females; 64.9% - 70.9% for males).

The T_{max} range was 0.50 – 8.0 h. The reliable terminal half-life t_{1/2,z} ranged between 3.0 and 4.0 h.

rhNGF exposure tended to be more than dose-proportionally increased at incrementing doses for male rats. For female rats, the exposure increase approached the dose-proportional increase with variability of the data.

No gender difference could be identified: the female / male exposure ratios were however variable.

After 4-week repeated administration, rhNGF exposure tended to be decreased or to be stable compared with day 1: the AUC_{0-t} week 4 / day 1 ratios ranged between 0.30 and 0.98. No accumulation of the test item was therefore observed.

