10.1.1 Pharmacokinetic endpoints

The kinetics of single dose administration as well as multiple dose assessment will be evaluated.

Beyond the respective rhNGF plasma levels for both ELISA methods, the following parameters will only be investigated for each ELISA method, if the data warrant to do so:

- maximum observed serum concentration (C_{max}), time to reach C_{max} (t_{max}), time elapsed between dosing and the first serum concentration that exceeds the assay quantification limit (t_{lag}) as measured without treatment based on assessments on D-1
- C_{max} , t_{max} , t_{lag} of single dose regimen based on assessments on D1 and pre-dose of D2
- C_{max} , t_{max} , t_{lag} of multiple dose regimen based on assessments starting with pre-dose of D2
- serum concentration measured before the administration of the next dose (C_{trough}) as assessed at pre-dose visit on D2, D3, D4, D5, D6
- $AUC_{[0-24]}$ for the single dose regimen and the first day of multiple dose regimen. $AUC_{[0-24]}$ as area under the serum concentration versus time curve from time 0 h to pre-dose value of the next day calculated by the linear trapezoidal rule. Values below the level of quantitation will be set to 0. Values below the baseline concentration will be set to zero other than for the values for which no later values above the baseline concentration are available, which will be set to missing.
- $AUC_{0-t_{last}}$ for the multiple dose regimen. This is derived as area under the serum concentration versus time curve from time 0 h to the last data point t_{last} after drug administration above the limit of quantitation and the baseline concentration, calculated by the linear trapezoidal rule.

Values below the baseline concentration will be set to zero other than for the values for which no later values above the baseline concentration are available, which will be set to missing

- AUC for the multiple dose regimen. AUC will be derived as area under the serum concentration versus time curve extrapolated to infinity, calculated as $AUC = AUC_{0-t_{last}} + C_{last}/\lambda_z$

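### The AUC[0-24] rule can delete the 24 h end point that its own definition requires, when Day -1 NGF is quantifiable and the 24 h value falls below it

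*SAP*

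**What the plan says.** SAP 7.2.17 gives the AUC[0-24] rule for the single-dose day and the first multiple-dose day. SAP 3.4 and Protocol 10.1.1 carry the same text. The bullet has three parts:

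- **Window and method:** the area runs "from time 0 h to pre-dose value of the next day calculated by the linear trapezoidal rule".
- **Below quantitation:** "Values below the level of quantitation will be set to 0". No exception is made for values at the end of the profile.
- **Below baseline:** these values also become zero, "other than for the values for which no later values above the baseline concentration are available, which will be set to missing".

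The third part appears again under AUC0-tlast. The PK parameters are based on the "difference between the measured rhNGF value after dosing and the value measured at the corresponding time on Day -1", so each subject's own Day -1 profile is the baseline. For the tables of time-matched change, SAP 7.2.17 uses a different substitution: "values below the limit of detection will be set to a value of 1 pg/ml".

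AUC is conditional on the data warranting it. SAP 7.2.17 allows for a PK appendix to be finalised before unmasking. Section 13 lists no appendices, section 12 lists no AUC table, and section 8.3.2 plans no imputation.

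**The concern.** Setting trailing below-baseline values to missing suits AUC0-tlast, which by definition stops at the last sample above baseline. It does not suit a window with a fixed end. The next-day pre-dose sample is the last one in the window, so if it is below baseline it is always a trailing value and is always removed. What remains is an area to tlast under the label AUC[0-24], and no instruction says how to compute the area without its end point.

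Two subjects with the same drug exposure can then be treated differently. One with a quantifiable Day -1 level who ends just below it loses the tail. One whose baseline and late samples are all below quantitation keeps zeros to 24 h. A subject who is never above a quantifiable baseline has no AUC at all, whereas the same absence of signal over an unquantifiable baseline taken as 0 gives an AUC of 0. At stake is whether the AUC[0-24] values in one summary are the same quantity for every subject.

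**Working it through.** The plan gives no AUC figure to reproduce, so the check applies the rule literally to example profiles.

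**Inputs**
- Sampling times from SAP 7.2.17: "for assessment of single dose scheme at D1 Pre-Dose, 0.5 hr, 2 hr, 4 hr, 8 hr", then 9, 10, 11, 12, 14 and 16 h, with the Day 2 pre-dose sample as 24 h.
- Linear trapezoidal rule on baseline-corrected values (SAP 7.2.17).
- Assumptions: a constant Day -1 level of 20 pg/ml; a quantitation limit of 15 pg/ml (the ELISA II detection limit, as no separate quantitation limit is given); illustrative concentrations.

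**Step 1: what is lost.** With trailing values at 0, everything after the first zero adds nothing. The difference between the two rules is one triangle:

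loss = 0.5 × Clast × (next sampling time − tlast)

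On Day 1 this is 0.5 × 8 = 4.0 × Clast for tlast 16 h, 0.5 × 4 = 2.0 × Clast for tlast 4 h, and 0.5 to 1.0 × Clast at the other times.

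**Step 2: three profiles with a quantifiable baseline** (corrected pg/ml; all later samples below baseline but quantifiable)

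| Corrected values from 0 h to tlast | tlast | Area under the plan's rule | Area with zeros to 24 h | Lost | Hours not covered |
|---|---|---|---|---|---|
| 0, 10, 30, 25, 15, 12, 10, 8, 6, 4, 2 | 16 h | 224 | 224 + 4.0 × 2 = 232 | 8/232 = 3.4% | 8 |
| 0, 10, 30, 25, 15, 12, 10, 8 | 11 h | 201 | 201 + 0.5 × 8 = 205 | 4/205 = 2.0% | 13 |
| 0, 10, 30, 10 | 4 h | 72.5 | 72.5 + 2.0 × 10 = 92.5 | 20/92.5 = 21.6% | 20 |

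Areas are in pg·h/ml. The third row in full: 2.5 + 30 + 40 = 72.5.

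**Step 3: which subjects are affected**
- *Baseline quantifiable, 24 h value quantifiable but below it:* end point deleted, as in step 2.
- *Baseline below quantitation and taken as 0, late values set to 0:* 0 is not below 0, so the end point stays. With 20, 40 and 25 pg/ml at 0.5, 2 and 4 h, the area is 5 + 45 + 65 + 50 = 165 under either rule.
- *The same profile with baseline carried as 1 pg/ml:* a late 0 is now below 1, so the tail is deleted. The area is 4.75 + 43.5 + 63 = 111.25, against 111.25 + 2.0 × 24 = 159.25 with zeros.
- *Baseline quantifiable, 24 h value below quantitation:* one sentence says 0, the other says missing, and no precedence is stated.
- *Never above a quantifiable baseline:* every value is trailing, so AUC is missing instead of 0.

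**Step 4: effect of noise.** Protocol 2.3 reports a rat terminal half-life that "ranged between 3.0 and 4.0 h". If that applied here, 2^(−24/3) = 0.4% to 2^(−24/4) = 1.6% of a single-dose level would remain at 24 h, so the sign of the 24 h difference would be mostly noise. I simulated the Day 1 times with half-life 3 or 4 h, a corrected peak of 2, 5 or 10 noise SDs, and symmetric noise of SD 1 on the corrected values. The 24 h value fell below baseline in 44–50% of profiles. Mean AUC, relative to the noise-free area, was 101–160% under the plan's rule and 104–170% with zero-filling. Over all profiles the two rules differed by 2–6%.

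**The case against.** The strongest objection is that little depends on this rule. AUC is conditional, descriptive and secondary, it has no listed table, and the possible PK appendix is a natural place to settle the detail. That stands, and it sets the priority. It does not resolve the contradiction, because the SAP states the rule now and no appendix is listed.

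A reader might infer that everyone who has cleared the drug loses the 24 h point. The documents do not support this. A subject whose baseline and late values are all below quantitation and taken as 0 keeps the full window. That group may be large: Protocol 2.6 says rhNGF was detectable in only 6 subjects in the earlier healthy-volunteer study, in which 58 were treated. On the other hand, ELISA II was added to improve sensitivity. Neither document gives endogenous levels.

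A reader might also infer that the rule understates exposure. It gives less than zero-filling, but zero-filling is not the truth: it removes negative noise and keeps positive noise. In the simulation the plan's rule was on average closer to the noise-free area in all six settings. The case for changing it is a consistent interval and definition, not recovery of lost exposure.

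**Conclusion.** The point holds as an internal contradiction. For subjects with a quantifiable Day -1 value and a 24 h value below it, the rule turns AUC[0-24] into an area to tlast, or leaves it missing if no sample exceeds baseline. Where the 24 h value is also below quantitation, the text gives two answers. Whether subjects with an undetectable baseline are affected depends on a substitution (0 or 1 pg/ml) that the plan does not specify for AUC.

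The numerical loss is usually small: 2.0% and 3.4% in the examples ending at 11 h and 16 h. It can be larger when tlast falls at 4 h, before the 4 h sampling gap (21.6% in the example). These percentages rest on assumed concentrations. The 44–50% frequency rests on a rat half-life and symmetric noise, applies only where baseline is quantifiable, and is not an estimate for this trial. The share of subjects affected cannot be obtained from the documents.

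It would go too far to say that a treatment-arm or single-dose versus Day 2 comparison of AUC is distorted: the SAP specifies no such contrast and plans no inferential analysis. Minor priority.

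**What to change.** In the PK appendix that SAP 7.2.17 allows for, before unmasking, with SAP 3.4 and Protocol 10.1.1 aligned:

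1. Limit set-to-missing to AUC0-tlast and the AUC to infinity built on it.
2. For AUC[0-24], set all below-baseline values to 0, including trailing ones and the 24 h value.
3. State that this rule and the below-quantitation rule both give 0, so no precedence question remains.
4. State whether a below-detection Day -1 value is taken as 0 or 1 pg/ml when AUC is derived.
5. State how an AUC of 0 enters the geometric mean and its confidence interval, since zero has no logarithm. The current text already needs this for subjects with no signal and an unquantifiable baseline taken as 0.

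The cost is a few sentences and no new data. There are two downsides. Zero-filling adds a small upward noise bias (104–170% of the noise-free area against 101–160% in the simulation). Subjects with no drug signal also enter the summary with an AUC of 0 instead of dropping out.
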